#### Gastrointestinal Toxicities

The most common site for ipilimumab-induced GI toxicity was the lower GI tract, and the most common presentation was mild to severe diarrhea or colitis with occasional bloody stools. In some cases, diarrhea began as mild and then worsened. Constipation was rarely associated with ipilimumab administration.

#### Liver Toxicities

Subjects receiving ipilimumab may develop elevations in LFTs in the absence of clinical symptoms. Occasionally, patients may present with symptoms, including right upper quadrant abdominal pain or unexplained vomiting.

#### **Endocrine** Toxicities

The most common inflammatory endocrine toxicities occurring in ipilimumab-treated subjects are hypophysitis and hypopituitarism. Secondary cortisol deficiency (hypoadrenalism), hypothyroidism or thyroiditis, and, less commonly, other endocrinopathies may occur concomitantly with hypophysitis; however, these may also present as the only or as primary endocrinopathy. Most patients with hypopituitarism presented with nonspecific complaints such as fatigue, visual field defects, confusion, or impotence. Some patients have had headache as the predominant presentation. The majority of subjects with hypopituitarism demonstrated enlarged pituitary glands based on brain magnetic resonance imaging (MRI). Low ACTH and cortisol were the most common biochemical abnormality; abnormal (mostly low) thyroid-stimulating hormone (TSH), free thyroxine (fT4), triiodothyronine (T3), testosterone, or prolactin have also been reported in some subjects.

#### Skin Toxicities

The most common inflammatory skin toxicities occurring in ipilimumab-treated subjects are rash and pruritus, mostly mild to moderate in severity. Two cases of fatal treatment-related toxic epidermal necrolysis have been reported in clinical trials. Postmarketing surveillance identified a fatal toxic epidermal necrolysis event in 1 subject who received ipilimumab after experiencing a severe or life-threatening skin adverse reaction on a prior cancer immune-stimulating therapy. Caution should be used when considering the use of ipilimumab in patients who have previously experienced a severe or life-threatening skin adverse reaction on a prior cancer immune-stimulating therapy.

#### Neurological Toxicities

Neurological manifestations in subjects treated with ipilimumab may include motor and/or sensory neuropathy. Given the difficulty in definitely establishing an inflammatory etiology, alternative

etiologies (eg, tumor progression) should be excluded. Fatal Guillain-Barre syndrome and cases of myasthenia gravis have been reported in clinical trials of ipilimumab. Unexplained motor neuropathy, muscle weakness, or sensory neuropathy should be evaluated, and noninflammatory causes such as disease progression, infections, metabolic disorders, and medications should be excluded.

## Other Toxicities

Ocular inflammation, manifested as Grade 2 or 3 episcleritis or uveitis, was associated with concomitant diarrhea in a few subjects (< 1%) and occasionally occurred in the absence of clinically apparent GI symptoms.

Other presumed inflammatory events reported include, but were not limited to, the following (individually reported for < 1% of subjects unless noted otherwise): arthritis/arthralgias, pneumonitis, pancreatitis, autoimmune (aseptic) meningitis, autoimmune nephritis, pure red cell aplasia, noninfective myocarditis, polymyositis, eosinophilia, pericarditis, urticaria (2%), large intestinal ulcer, esophagitis, acute respiratory distress syndrome, renal failure, infusion reactions, and MG.

## **12. ADVERSE EVENTS**

## 12.1 Definitions

## 12.1.1 Adverse Event (AE)

An AE is any untoward medical occurrence whether or not considered related to the study drug that appears to change in intensity during the course of the study. The following are examples of AEs:

- Unintended or unfavorable sign or symptom
- A disease temporally associated with participation in the protocol
- An intercurrent illness or injury that impairs the well-being of the subject

Abnormal laboratory values or diagnostic test results constitute AEs only if they induce clinical signs or symptoms or require treatment or further diagnostic tests

Hospitalization for elective surgery or routine clinical procedures that are not the result of an AE (e.g., surgical insertion of central line) should not be recorded as an AE.

Disease progression should not be recorded as an AE, unless it is attributable to the study regimen by the site investigator.

## 12.1.2 Serious Adverse Event (SAE)

An SAE is an adverse event that:

- Results in death. NOTE: Death due to disease progression should not be reported as a SAE, unless it is attributable by the site investigator to the study drug(s)
- Is life-threatening (defined as an event in which the subject was at risk of death at the time of the event; it does not refer to an event which hypothetically might have caused death if it were more severe)
- Requires inpatient hospitalization for >24 hours or prolongation of existing hospitalization. **NOTE:** Hospitalization for anticipated or protocol specified procedures such as administration

of chemotherapy, central line insertion, metastasis interventional therapy, resection of primary tumor, or elective surgery, will not be considered serious adverse events.

- Results in persistent or significant disability/incapacity
- Is a congenital anomaly or birth defect
- Is an important medical event (defined as a medical event(s) that may not be immediately lifethreatening or result in death or hospitalization but, based upon appropriate medical and scientific judgment, may jeopardize the subject or may require intervention (e.g., medical, surgical) to prevent one of the other serious outcomes listed in the definition above). Examples of such events include, but are not limited to, intensive treatment in an emergency room or at home for allergic bronchospasm; blood dyscrasias or convulsions not resulting in hospitalization; or the development of drug dependency or drug abuse.

## **12.1.3 Unexpected Adverse Event**

For this study, an AE is considered unexpected when it varies in nature, intensity or frequency from information provided in the current IB, package insert, or when it is not included in the informed consent document as a potential risk. Unexpected also refers to AEs that are mentioned in the IB as occurring with a class of drugs or are anticipated from the pharmacological properties of the drug, but are not specifically mentioned as occurring with the particular drug under investigation.

## 12.1.4 Relatedness

AEs will be categorized according to the likelihood that they are related to the study drug(s). Specifically, they will be categorized using the following terms:

Unrelated	The Adverse Event is not related to the drug(s)
Unlikely	The Adverse Event is doubtfully related to the drug(s)
Possible	The Adverse Event may be related to the drug(s)
Probable	The Adverse Event is likely related to the drug(s)
Definite	The Adverse Event is clearly related to the drug(s)

## 12.1.5 Pregnancy

If, following initiation of the study drugs, it is subsequently discovered that a subject is pregnant or may have been pregnant at the time of study drug exposure, including during at least 6 half-lives after study drug administration, the study drug will be permanently discontinued in an appropriate manner (e.g., dose tapering if necessary for subject safety).

The site investigator must immediately notify BTCRC AHQ who will then notify Worldwide Safety @BMS of this event via the Pregnancy Form in accordance with SAE reporting procedures.

Follow-up information regarding the course of the pregnancy, including perinatal and neonatal outcome and, where applicable, offspring information must be reported on the Pregnancy Form [provided upon request from BMS].

Any pregnancy that occurs in a female partner of a male study participant should be reported to BMS. Information on this pregnancy will be collected on the Pregnancy Form.

## 12.1.6 Overdose

An overdose is defined as the accidental or intentional administration of any dose of a product that is, in the judgement of the treating physician, considered both excessive and medically important. All occurrences of overdose must be reported as a SAE.

## 12.2 Reporting

## 12.2.1 Adverse Events

- AEs will be recorded from time of signed informed consent until 100 days after discontinuation of study drug(s) or until a new anti-cancer treatment starts, whichever is earlier.
- AEs will be recorded regardless of whether or not they are considered related to the study drug(s).
- All AEs will be recorded in the subject's medical record and on the appropriate study specific eCRF form within OnCore.
- All AEs considered related to study drug(s) will be followed until resolution to ≤ Grade 1 or baseline, deemed clinically insignificant, and/or until a new anti-cancer treatment starts, whichever occurs first.
- Asymptomatic laboratory abnormalities that do not require treatment will not be collected as adverse events.

## 12.2.2 Serious Adverse Events (SAEs)

## 12.2.2.1 Site Requirements for Reporting SAEs to BTCRC Administrative Headquarters

- SAEs will be reported from time of signed informed consent until 100 days after discontinuation of study drug(s) or until a new anti-cancer treatment starts, whichever is earlier.
- SAEs will be reported on the SAE Submission Form and entered in the SAE tab in OnCore within 1 business day of discovery of the event.
- SAEs include events related and unrelated to the study drug(s).
- All SAEs will be recorded in the subject's medical record and on the appropriate study specific eCRF form(s) within OnCore.
- All SAEs regardless of relation to study drug will be followed until resolution to ≤ Grade 1 or baseline and/or deemed clinically insignificant and/or until a new anti-cancer treatment starts, whichever occurs first.

The site will submit the completed SAE Submission Form (see Documents/Info tab of the EDC) to BTCRC AHQ within **1 business day** of discovery of the event. The form may be sent electronically to [contact]. The site investigator is responsible for informing the IRB and/or other local regulatory bodies of the SAE as per local requirements.

The original copy of the SAE Submission Form and the email correspondence must be kept within the study file at the study site.

Once the SAE has resolved, sites must submit a follow up SAE Submission Form within a reasonable timeframe to BTCRC AHQ electronically at [contact].

## 12.2.2.2 BTCRC AHQ Requirements for Reporting SAEs to BMS

BTCRC AHQ will report all SAEs to BMS within **1 business day** of receipt of the SAE Reporting Form from a site. Follow-up information will be provided to BMS as it is received from a site.

Contact information for sending SAE information to BMS:

SAE Email Address: [contact] SAE [contact]

## 12.2.2.3 Sponsor-Investigator Responsibilities

BTCRC AHQ will send a SAE summary to the sponsor-investigator **within 1 business day** of receipt of SAE Submission Form from a site. The sponsor-investigator will promptly review the SAE summary and assess for expectedness and relatedness.

## 12.2.2.4 BTCRC AHQ Responsibilities for Reporting SAEs to FDA

BTCRC AHQ has been designated to manage the Investigational New Drug Application (IND) associated with this protocol on behalf of the sponsor-investigator. BTCRC AHQ will cross-reference this submission to BMS's parent IND at the time of submission. Additionally, BTCRC AHQ will submit a copy of these documents to BMS at the time of submission to FDA.

BTCRC AHQ will be responsible for all communication with the FDA in accordance with 21CFR312 which includes but is not limited to the 7 and 15 Day Reports, as well as an Annual Progress Report. Additionally, BTCRC AHQ will submit a copy of the 7 and 15 Day Reports and the Annual Progress reports to BMS at the time of submission to FDA.

## 12.2.2.5 IND Safety Reports Unrelated to this Trial

BMS will provide BTCRC AHQ with IND safety reports from external studies that involve the study drug(s) per their guidelines. BTCRC AHQ will forward the safety reports to the sponsor-investigator who will review these reports and determine if revisions are needed to the protocol or consent. BTCRC AHQ will forward these reports to participating sites **within 1 business day** of receiving the sponsor-investigator's review. Based on the sponsor-investigator's review, applicable changes will be made to the protocol and informed consent document (if required). All IND safety reports will also be made available to sites via OnCore.

Upon receipt from BTCRC AHQ, site investigators (or designees) are responsible for submitting these safety reports to their respective IRBs, as per their IRB policies.

## **13. STATISTICAL METHODS**

Statistical analysis of this study will be the responsibility of the Department of Biostatistics at Indiana University School of Medicine. Parameter estimates and relevant summary statistics will be reported for both efficacy and safety outcomes. Continuous variables will be summarized by means, medians, minima, maxima, and standard deviations. Categorical variables will be summarized by frequencies and percentages. Missing data will not be imputed. Additional exploratory analysis will be conducted when appropriate. Changes from the analysis plan will not require an amendment to the protocol unless it changes a significant feature in the protocol; however all changes from the original analysis plan will be documented in the final study report. The statistical analysis methods are outline below.

## 13.1 Study Design

This is a two-arm 1:1 randomized non-comparative Phase II study of consolidation immunotherapy with nivolumab and ipilimumab or nivolumab alone following concurrent chemoradiotherapy for unresectable stage IIIA/IIIB NSCLC. Randomization will be stratified by stage (IIIA vs. IIIB) and histology (squamous vs. non-squamous vs. NOS). The two arms will not be compared statistically.

## 13.2 Endpoints

## **13.2.1 Definition of Primary Endpoint**

• PFS is defined as the time from randomization until the criteria for disease progression is met as defined by RECIST 1.1 or death as a result of any cause.

## 13.2.2 Definition of Secondary Endpoints

- Overall survival will be defined as the time from randomization until death from any cause.
- Time to metastatic disease will be defined as the time from randomization until evidence of disease outside of the radiated field.
- Toxicities will be defined by the NCI Common Terminology Criteria for Adverse Events (NCI CTCAE) v4.

## 13.3 Sample Size and Accrual

This is a non-comparative two-arm trial with each arm being analyzed separately. For Arm 1, when the sample size is 51, a non-parametric test (single-group and based on a non-parametric estimate of the cumulative hazard function) with a one-sided 0.10 significance level will have 80% power to detect an 18 month PFS rate of 44% relative to a historical control rate of 30% (similar to the PACIFIC trial) assuming an accrual period of approximately 24 months and maximum follow-up of 48 months (i.e. would allow for up to 24 months of follow-up after accrual ends). For Arm 2, when the sample size is 48, a non-parametric test (as above) with a one-sided 0.10 significance level will have 80% power to detect an 18 month PFS of 59% relative to a historical control rate of 44% (similar to the PACIFIC trial in the checkpoint inhibitor arm and a 15% increase in absolute magnitude) assuming an accrual period of approximately 24 months. To account for non-evaluable subjects (5%), 54 subjects will be enrolled in Arm 1 and 51 subjects in Arm 2.

## 13.4 Analysis Datasets

Population	Definition
Enrolled	This will comprise all subjects who meet the eligibility criteria and are registered onto the study.
Evaluable	This will comprise all subjects who receive at least one dose of trial drug and either undergo at least one post-baseline assessment or die before any evaluation.
Safety	This will comprise all subjects that take a least one dose of either drug.

## 13.5 Assessment of Safety

Toxicities will be defined by the NCI Common Terminology Criteria for Adverse Events (NCI CTCAE) v4.

## **13.6** Assessment of Efficacy

PFS, OS and Time to metastatic disease will be assessed with RECIST 1.1.

#### 13.7 Data Analysis Plans

## 13.7.1 Analysis Plans for Primary Objective

For the primary endpoint, PFS at 18 months, each arm will be separately compared to the historical control rate of 30% for Arm 1 and 44% for Arm 2 using a one-sided Sign Test for censored data (36) in the randomized population. PFS overall will be estimated with a Kaplan-Meier curve and 80% confidence interval.

## 13.7.2 Analysis Plans for Secondary Objectives

OS will be estimated using a Kaplan-Meier curve and 95% confidence intervals for the OS medians in the randomized population. The cumulative incidence for time to metastatic disease will be calculated with those dying from causes other than metastatic disease as a competing risk, and right censoring for patients alive and without metastases. Safety will be assessed in the Safety population. Separate frequency tables will be generated for each arm.

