STATISTICAL CONSIDERATIONS	
 
hepatitis C or human immunodeficiency virus (see protocol for exceptions).
 
14. History or current evidence of any condition, therapy, or laboratory abnormality that might confound the results of the trial, interfere with the subject's participation for the full duration of the trial, or is not in the best interest of the subject to participate, in the opinion of the site investigator.
 
15. Has a known history of active TB (Bacillus Tuberculosis).
 
16. Hypersensitivity to nivolumab, ipilimumab, or any of their excipients.
 
17. Has received a live vaccine within 30 days prior to planned start of study therapy.
 
NOTE: Seasonal influenza vaccines for injection are generally inactivated flu vaccines and are allowed; however intranasal influenza vaccines (e.g., Flu-Mist®) are live attenuated vaccines, and are not allowed.
 
This is a non-comparative two-arm trial with each arm being analyzed separately. For Arm 1, when the sample size is 51, a non-parametric test (single-group and based on a non-parametric estimate of the cumulative hazard function) with a one-sided 0.10 significance level will have 80% power to detect an 18 month PFS rate of 44% relative to a historical control rate of 30% (similar to the PACIFIC trial) assuming an accrual period of approximately 24 months and maximum follow-up of 48 months (i.e. would allow for up to 24 months of follow-up after accrual ends). For Arm 2, when the sample size is 48, a non-parametric test (as above) with a one-sided 0.10 significance level will have 80% power to detect an 18 month PFS of 59% relative to a historical control rate of 44% (similar to the PACIFIC trial in the checkpoint inhibitor arm and a 15% increase in absolute magnitude) assuming an accrual period of approximately 24 months and maximum follow-up of 48 months. To account for non-evaluable subjects (5%), 54 subjects will be enrolled in Arm 1 and 51 subjects in Arm 2. Time to metastatic disease and Overall survival will be estimated with Kaplan-Me

TOTAL	Cox regression methods.
NUMBER OF SUBJECTS	N = 105 (54  subjects in Arm 1 and 51 in Arm 2)
ESTIMATED ENROLLMENT PERIOD	24 months
ESTIMATED STUDY DURATION	48 months

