#### 2.2.2 Secondary Endpoints

- Overall survival will be defined as the time from randomization until death from any cause.
- Time to metastatic disease will be defined as the time from randomization until evidence of disease outside of the radiated field.
- Toxicities will be defined by the NCI Common Terminology Criteria for Adverse Events (NCI CTCAE) v4.

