#### 6.2 Subject Withdrawal/Discontinuation Criteria

Subjects may withdraw consent at any time for any reason or be withdrawn from the trial at the discretion of the site investigator should any untoward effect occur. In addition, a subject may be withdrawn by the sponsor-investigator or BTCRC if enrollment into the trial is inappropriate, the trial plan is violated, or for administrative and/or other safety reasons. Specific details regarding discontinuation or withdrawal are provided below.

A subject must be discontinued from the trial treatment for any of the following reasons:

- Confirmed radiographic disease progression by RECIST 1.1 criteria
- Unacceptable adverse experiences as described in Section 5.3 and 11.1

- Intercurrent illness that prevents further administration of treatment
- Site investigator's decision to withdraw the subject
- A female subject has a confirmed positive serum/urine pregnancy test
- Noncompliance with trial treatment or procedure requirements
- Completed 6 months of treatment with protocol therapy
- Subject refuses further treatment
- If a subject has a treatment delay of more than 12 weeks from last infusion. See section 6.1.

A subject must be discontinued from the trial for any of the following reasons:

- Administrative reasons
- The subject or legal representative (such as a parent or legal guardian) withdraws consent.
- The subject is lost to follow-up

The End of Treatment and Follow-up visit procedures are listed in Section 7 (Study Schedule of Events and Visit Requirements). After the end of treatment, each subject will be followed for 100 days for adverse event monitoring (serious adverse events will be collected for 100 days after the end of treatment as described in Section 12.2.2). Subjects who discontinue for reasons other than progressive disease will have post-treatment follow-up for disease status until disease progression, initiating a non-study cancer treatment, withdrawing consent or becoming lost to follow-up. After documented disease progression each subject will be followed for survival for up to 2 years, withdrawal of consent, or the end of the study, whichever occurs first.

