- 10. Screening scan including at least CT portion of the chest and abdomen must be performed within 56 days after the completion of chemoradiation or consolidation. PET CT may be done in place of regular CT scans at the discretion of the site investigator. Baseline scans should be done within 28 days prior to treatment initiation. Radiographic disease assessment will be done every 12 weeks ± 4 weeks during study treatment. The scan interval may be reset if scans were done early for clinical reasons. See also 8.3.
- 11. After completion of protocol therapy, subjects who discontinue for reasons other than progressive disease will have post-treatment follow-up for disease status until disease progression, initiating a non-study cancer treatment, withdrawing consent or becoming lost to follow-up. Post treatment radiographic disease assessment should be performed every 3 months until progression. After documented disease progression each subject will be followed for survival every 3 months for up to 2 years, withdrawal of consent, or the end of the study (whichever occurs first).
- 12. A head MRI or CT should be done prior to study treatment for subjects that are symptomatic or have not had prior brain imaging.
- 13. For subjects who meet all eligibility criteria and have recovered sufficiently from treatment with chemoradiation, initial consolidation therapy with nivolumab will be started within 56 days after chemoradiation is complete. For subjects who meet all eligibility criteria after completion of up to two consolidation chemotherapy treatments, therapy with nivolumab will be started within 56 days after last cycle of chemotherapy.
- 14. Mandatory submission of unstained slides from an archived tumor block (if available) for PD-L1, CD4, CD8 by IHC. In addition, whole exome sequencing, RNA sequencing, methylation analysis will be performed. See Correlative Laboratory Manual (CLM) for collection, labeling and shipping instructions.
- 15. Mandatory blood samples for correlative testing should be drawn pre-treatment on C1D1, C2D1 and either at the End of Treatment Visit or if the subject develops any grade 3-4 pneumonitis. See CLM for collection, labeling, and shipping instructions.
- 16. If subject has a bronchoscopy with BAL for clinical reasons, please collect a portion of the of BAL fluid for correlative analysis (optional).

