## 8.5 Long Term Follow-up Evaluations

After completion of protocol therapy, subjects who discontinue for reasons other than progressive disease will have post-treatment follow-up for disease status until disease progression, initiating a non-study cancer treatment, withdrawing consent or becoming lost to follow-up. After documented disease progression each subject will be followed for survival every 3 months ( $\pm$  4 weeks) for up to 2 years, withdrawal of consent, or the end of the study (whichever occurs first).

• Treatment-related adverse events will be followed until resolution, return to baseline, or deemed clinically insignificant. Adverse events (from time of consent) and concomitant medications (28 days prior to start of protocol treatment) should be assessed and recorded until 100 days after last

dose of study drug or until a new anti-cancer treatment starts, whichever is earlier. SAE's and the conmeds used to treat them will be collected up to 100 days post treatment.

• For subjects who discontinue for reasons other than progressive disease, radiographic disease assessment should be performed every 3 months for up to 2 years until progression, initiating a non-study cancer treatment, withdrawing consent or becoming lost to follow-up. The scan interval may be reset if scans were done sooner for clinical reasons. PET CT may be done in place of regular CT scans at the discretion of the site investigator. This imaging may be done locally. Once patients are off treatment and on follow-up, the window for imaging is ±4 weeks.

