## **10.8.7** Time to Metastatic Disease

From date of randomization until the date of metastatic disease outside of the radiated field. Subjects who have not metastasized will be right censored

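### Time to metastatic disease: protocol imaging stops at in-field progression with no stated handling or censoring date, and the synopsis and Section 10.8.7 do not match the competing-risk estimator in Section 13.7.2

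*Combined protocol and SAP*

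**What the plan says.** **Event.** Section 2.2.2 states: "Time to metastatic disease will be defined as the time from randomization until evidence of disease outside of the radiated field". Sections 10.8.7 and 13.2.2 agree. In-field progression is therefore not an event for this endpoint.

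**Follow-up.** Under Section 6.2, subjects who stop treatment for reasons other than progression "will have post-treatment follow-up for disease status until disease progression, initiating a non-study cancer treatment, withdrawing consent or becoming lost to follow-up". The Arm 1 calendar footnotes add: "Post treatment radiographic disease assessment should be performed every 3 months until progression". The Arm 2 footnotes say the same, and neither separates in-field from distant progression. Section 8.5 then provides: "After documented disease progression each subject will be followed for survival every 3 months", for up to 2 years.

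**Analysis.** Section 13.7.2 calls for a cumulative incidence with "those dying from causes other than metastatic disease as a competing risk, and right censoring for patients alive and without metastases". It gives no censoring date. Section 10.8.7 says "Subjects who have not metastasized will be right censored", with no competing event and no date. By contrast, Sections 10.8.5 and 10.8.6 name the last disease evaluation as the censoring date for time to progression and PFS. The readable part of the synopsis says "Time to metastatic disease and Overall survival will be estimated with Kaplan-Me", where the text breaks off.

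**The concern.** A subject with in-field failure can still metastasise, but the protocol schedules no further scan to find it. Section 13.7.2 then counts that subject as a competing death if they die, or as censored if alive. The plan says neither when such a subject leaves the risk set nor whether an unexamined subject counts as metastasis-free. Depending on the answer, the estimate suffers from missed events, from informative censoring, or from both. Separately, the estimator depends on which section is read.

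This is a named secondary endpoint in both arms. Section 2.1.2 sets it against historical controls, and Section 14.4 requires the result to be posted. The primary endpoint is not affected.

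**Working it through.** The documents give no metastasis rate, so there is no planned figure to reproduce. What follows is an illustration on assumed constant monthly hazards.

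**Assumptions.** From the event-free state: metastasis m = 0.025, in-field progression a = 0.015, death d = 0.005, total L = 0.045. After in-field failure: metastasis k × m with k from 1 to 3, and death d1 = 0.03 to 0.04. No metastasis is ascertained after in-field failure.

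**Scale check.** exp(−0.045 × 18) = 44.5%, close to the 44% 18-month PFS hypothesised for Arm 1. By 18 months, (0.015/0.045) × (1 − 0.445) = 18.5% of subjects have failed in-field first, about 10 of 54.

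**1. Literal reading, subjects followed as metastasis-free to last contact.** Estimate = (m/L)(1 − exp(−Lt)).
- 18 months: 0.5556 × 0.5551 = 30.8%.
- 24 months: 0.5556 × 0.6604 = 36.7%.

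**2. Literal reading, living in-field progressors censored at progression and later deaths kept as competing events.** This was simulated with 400,000 subjects per scenario and follow-up uniform on 24 to 48 months. The result is about 32% at 18 months and 38% to 39% at 24.

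**3. True incidence.** Add to step 1 the metastases that follow in-field failure. With r = km + d1, the addition is a·km/(r − L) × [(1 − exp(−Lt))/L − (1 − exp(−rt))/r]. At 18 months with d1 = 0.03:
- k = 1: 0.0375 × (12.34 − 11.43) = 3.4 points, total 34.3%.
- k = 3: 0.01875 × (12.34 − 8.08) = 8.0 points, total 38.8%.

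Over the full grid the true value is about 34% to 39% at 18 months and 41% to 48% at 24.

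**4. Everyone censored at the last scan.** Estimate = m/(m + d) × (1 − exp(−(m + d)t)).
- 18 months: 0.8333 × (1 − exp(−0.54)) = 34.8%.
- 24 months: 0.8333 × (1 − exp(−0.72)) = 42.8%.

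At 18 months this is about half a point high when k = 1 and 4 points low when k = 3. At k = 0.5 the true value is about 32.6%, so it is about 2 points high.

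**5. Kaplan-Meier with deaths censored.** On the step 4 data, 1 − exp(−mt) gives 36.2% and 45.1%, about 1.5 and 2.3 points above the competing-risk estimate. Under the step 2 rule the gaps are about 2 and 3.5 points.

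**6. Second scaling, 24 months.** Take the hypothesised 18-month PFS of 44% (Arm 1) and 59% (Arm 2). Assume in-field progression is 30% to 60% of first PFS events, death without metastasis 10%, d1 = 0.04, and k = 0.5, 1 or 2.
- Subjects kept at risk as metastasis-free: low in every scenario, by about 1 to 10 points.
- Censored at the last scan: from about 3 points low to 4 points high.

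| In-field share 45%, k = 1 | True | Kept at risk | Last-scan censoring |
|---|---|---|---|
| PFS 44% | 35.4% | 29.9% | 37.0% |
| PFS 59% | 25.4% | 22.7% | 26.3% |

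**The case against.** A reader might infer that the incidence will be biased low. The documents do not go that far. The neighbouring definitions in Sections 10.8.5 and 10.8.6 censor at the last disease evaluation. If that rule is carried over, an in-field progressor leaves the risk set at the last scan and the direction is undetermined (steps 4 and 6). This stands. The counterweight is that Section 13.7.2 makes non-metastatic deaths competing events without exception, and survival follow-up will observe deaths after in-field progression. Last-scan censoring of everyone would discard those deaths, so the literal text leans towards understatement without settling it.

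A reader might also infer that the result will look favourable against the historical control. Section 2.1.2 states that aim, but Section 13.7.2 plans estimation only. No historical metastasis figure appears, and the documents do not say whether the control trial kept scanning after local progression.

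The shifts are also modest beside sampling error. With 54 subjects, the 95% half-width around 34% is 1.96 × √(0.34 × 0.66/54), about 13 points. Metastases learned of through routine care would narrow the gap, although no section requires their dates to be collected for this endpoint.

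On the estimator, the synopsis sentence is cut off, and Section 10.8.7 is a definition that names no method. Section 13.7.2 is the detailed plan and its competing-risk approach is sound. Aligning the other two is largely editorial, but Section 10.8.7 and Section 13.7.2 are both intact and treat deaths differently.

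**Conclusion.** The point holds as a gap in ascertainment and specification, not as a demonstrated downward bias. Imaging stops while in-field progressors remain at risk of the event, and neither their handling nor a censoring date is stated. In the main illustration, the literal readings of Section 13.7.2 fall roughly 2 to 8 points short at 18 months (31% to 32% against 34% to 39%). Censoring at the last scan gives about 35%, which can be too high or too low. These sizes rest wholly on assumed hazards and on no ascertainment after in-field failure. The estimator mismatch is worth about 1.5 to 2 points at 18 months and 2.3 to 3.5 at 24, depending on the censoring rule. The correction is worth making because it is cheap, and the consequences are confined to a secondary endpoint.

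**What to change.** 1. Use the competing-risk cumulative incidence of Section 13.7.2 in the synopsis and Section 10.8.7 as well.
2. Keep the endpoint as defined. At the existing 3-monthly survival contacts, record the date of first out-of-field disease known from routine care. Those contacts are written for subjects with documented progression, so say whether subjects who start non-study treatment without progression are covered too.
3. State the censoring date as the last assessment of metastatic status, and say how a death after in-field progression with no later assessment is classified.
4. As a sensitivity analysis, report the cumulative incidence of out-of-field disease as first failure, with in-field progression and death as competing events. Protocol follow-up already captures all three. This should not replace the main analysis, because it answers a different question from the defined endpoint.

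The cost is protocol and SAP wording, one data item at contacts already planned, and one extra analysis. No scans are added. Ascertainment from routine care will be less complete than from protocol imaging, and the report should say so.
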